1.0 Objectives / Specific Aims

Aim 1: To determine if combined acoustic vibration and oscillating expiratory pressure impacts exhaled nasal Nitric Oxide (NO) in healthy controls as a potential mechanism

Aim 2: To determine the safety and efficacy of combined acoustic vibration and oscillating expiratory pressure for treatment of eustachian tube dysfunction (ETD).

Aim 3: To determine the safety and efficacy of combined acoustic vibration and oscillating expiratory pressure for treatment of sinus pain/pressure

2.0 Background

Eustachian tube dysfunction (Meyer TA, etal) and sinus pain/pressure impact the quality of life of millions of Americans (Falco JJ, etal). It is thought that these disorders may be due to positive or negative pressure differential between the middle ear or paranasal sinuses. Current treatment options for ETD and sinus pressure/pain are typically Valsalva (positive expiratory pressure) with the hopes of equalizing pressures between the middle ear space or paranasal sinuses and the nasal cavity/external environment. Pharmacologically, nasal steroid sprays can be used to try to open the ET and sinus drainage pathways. If this fails, then procedures to include pressure equalization tubes (PETs) or balloon eustachian tube/paranasal sinus dilation are offered.

Future treatment options: This study aims to test the safety, efficacy and potential mechanism of action of the SinuSonic device on adults with ETD or facial pain/pressure. SinuSonic is a medical device that utilizes sound and pressure combined with normal breathing. It has been shown to be safe and relieve nasal congestion (Soler ZM, etal). The study will have 3 aims. Aim 1 will examine healthy controls with no signs of upper respiratory infection, inflammation, or ETD to determine if exhaled nasal NO is increased. Acoustic energy (humming) has been shown to increase nasal NO dramatically, thus equalization of gas pressures between the middle ear, the paranasal sinuses and the nasal cavity may very well explain any efficacy noted. Aim 2 will be performed to examine therapeutic efficacy for ETD. Aim 3 will be performed to examine therapeutic efficacy for sinus pain/pressure.

3.0 Intervention to be studied

Aim 1: Exhaled NO in healthy controls (N=10)

- Initial intervention: Baseline exhaled nasal NO will be measured using a clinically available nasal airflow sampling device at rest. Then using SinuSonic devices for 2 exhalations followed by the 30 second NO sampling period. We will use 4 SinuSonic devices with frequencies between 64Hz and 2,000Hz in random order. Five minutes rest will be allowed between trials. The final trial will use 128 Hz for 1 minute.

Aim 2: Clinical efficacy in subjects with ETD (N=30)

- Baseline: Subjects will complete ETD questionnaire to confirm eligibility. Tympanogram will be completed. After confirming eligibility, subjects will use the SinuSonic device for 3 minutes in the clinic setting. Immediate treatment effect will be assessed with questionnaires.
- Primary timepoint: Subjects will use SinuSonic device twice daily for 3 minutes in the home setting for 6 weeks. Tympanogram and ET questionnaires will be completed.

Aim 3: Clinical efficacy in subjects with sinus pain/pressure (N=30)

- Baseline: Subjects will complete VAS to confirm eligibility. After confirming eligibility, subjects will use the SinuSonic device for 3 minutes in the clinic setting. Immediate treatment effect will be assessed with questionnaires.
- Primary timepoint: Subjects will use SinuSonic device twice daily for 3 minutes in the home setting for 4 weeks. Questionnaires will be completed at 2 weeks and 4 weeks.

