3.1 Device Instructions

Instructions for use:

1. Hold the SinuSonic device at a 45-degree angle
2. Deep breathe

3. Hold the SinuSonic to your nose and blow out into the mask of the SinuSonic. The goal here is to hear the “target flutter” sound that is desired during treatment with the SinuSonic
4. Put the device over the nose using the nasal mask
5. Breathe in and out thru the nose if possible. If nasal breathing is not possible it is ok to open mouth to breathe in and try and hear the “target flutter” sound when you breathe out
6. You will feel a little resistance to breathe out and a vibration sensation from a speaker in the device
7. Remove the device to “blow the nose” if nasal drainage occurs
8. Return the device to the nose then breathe in and out thru the nose to try and hear the “target flutter” sound
9. Time of use is 3 minutes of nasal breathing with the device - as tolerated

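### Aim 1 compares nasal NO at rest, always measured first, with NO after exhalations through the device, so a rise shows an effect of device use as a whole and cannot be credited to vibration and oscillating pressure apart from the breathing manoeuvre, mask and order

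*Combined protocol and SAP*

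**What the plan says.** Section 1.0 states Aim 1 for the combined stimulus: "To determine if combined acoustic vibration and oscillating expiratory pressure impacts exhaled nasal Nitric Oxide (NO) in healthy controls as a potential mechanism". Section 2.0 supplies the rationale, which is acoustic: "Acoustic energy (humming) has been shown to increase nasal NO dramatically".

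Section 3.0 sets the sequence. The reference comes first: "Baseline exhaled nasal NO will be measured using a clinically available nasal airflow sampling device at rest". The device readings follow: "Then using SinuSonic devices for 2 exhalations followed by the 30 second NO sampling period". On the conditions it says "We will use 4 SinuSonic devices with frequencies between 64Hz and 2,000Hz in random order", with five minutes of rest between trials, and then "The final trial will use 128 Hz for 1 minute".

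The general instructions in section 3.1 call for a deep breath and then say "Hold the SinuSonic to your nose and blow out into the mask of the SinuSonic". Section 3.2 describes a flutter valve that provides gentle oscillating resistance on expiration.

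For Aim 1, section 10.0 names two comparisons: baseline against a 10-second reading and baseline against a 3-minute reading. The Aim 1 form in the appendices has fields for a resting peak, a 10-second peak and a 3-minute peak, and none for frequency. No sound-off, sham, valve-only or matched-exhalation condition appears in section 3.0, the schedule in 9.1, section 10.0 or the Aim 1 form.

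**The concern.** Several things change together between the reference and every device reading: the subject performs instructed exhalations, wears a mask, breathes out against the valve, receives sound, and is measured later in the visit. Vibration and oscillating pressure are the stimulus named in Aim 1. The manoeuvre, the mask and the order of readings are not.

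Aim 1 is there to support a mechanism for whatever is seen in Aims 2 and 3. If two exhalations by themselves alter the NO sampled over the next 30 seconds, or if readings drift over the visit, the planned comparison could be positive with no contribution from the named stimulus. It would also look the same whether or not sound played any part, although sound is what the Background puts forward.

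**Working it through.** The plan gives no effect size, standard deviation or power for Aim 1, so there is no figure to reproduce. The check is of what each contrast estimates, followed by an illustration under assumed values.

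**1. What each contrast contains.** Write a device reading minus the resting reading as a sum of parts (additivity is an assumption): M, the exhalation manoeuvre; K, the mask; O, order or time in the visit; P, oscillating pressure; A, sound.

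| Contrast | Estimates | In the plan? |
|---|---|---|
| Device minus rest (rest always first) | M + K + O + P + A | Yes, the only kind named in 10.0 |
| Device minus matched breathing, order randomised | K + P + A | No |
| Sound-on minus sound-off, order randomised | A | No |
| Frequency f minus frequency g, order randomised | A(f) − A(g) | Trials are run, contrast not named |

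Aim 1 asks about P + A. The planned contrast adds M + K + O. Randomising the frequencies balances order among the four devices, but not between them and the resting reading. The 1-minute trial at 128 Hz has a fixed place at the end, so its comparison with rest also carries O.

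**2. What the frequencies can show.** If valve and manoeuvre are the same across the four devices, M, K and P cancel and randomisation balances O. A difference between frequencies would then point to sound. If all four raise NO equally, A(f) − A(g) = 0. That fits both no acoustic effect and an equal acoustic effect at every frequency.

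**3. Illustration.** Inputs from the documents: n = 10 (section 5.0) and a significance level of 0.05 without correction (section 10.0). Assumed: a two-sided paired t-test, and a total b for the parts not of interest, in units of the SD of paired differences. The effect of interest is set to zero. With 9 degrees of freedom and noncentrality b × √10, the chance that the planned contrast is significant is:

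| b (assumed) | b × √10 | Device vs rest | Sound-on vs sound-off | Across 4 frequencies |
|---|---|---|---|---|
| 0 | 0 | 0.05 | 0.051 | 0.050 |
| 0.5 | 1.58 | 0.29 | 0.050 | 0.049 |
| 1.0 | 3.16 | 0.80 | 0.051 | 0.049 |
| 1.5 | 4.74 | 0.99 | 0.051 | 0.050 |

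The device-versus-rest column comes from the noncentral t distribution. The last two come from 20,000 simulated trials with independent errors of equal variance, the last as a repeated-measures ANOVA across frequencies. For the acoustic question, b stands for M + K + O + P. For the combined question, b in the device-versus-rest column stands for M + K + O only.

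The table shows how the contrasts behave, not what this trial will find. The documents do not give b, and nothing in them fixes its sign.

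**The case against.** The strongest reply is that Aim 1 asks about the combination, and rest against the whole device broadly answers that. This stands in part. A reader might infer that acoustic vibration alone is the mechanism under test and that the whole effect of exhaling against resistance is bias. Section 1.0 does not support that: oscillating expiratory pressure is part of the named stimulus, so the valve's effect belongs to the effect being estimated. The manoeuvre, the mask and the order of readings remain.

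A reader might also picture quiet rest set against deep, forced breathing. The plan says only that the reference is taken at rest. The deep breath is in the general instructions, which describe a 3-minute use and not Aim 1's two exhalations, and section 2.0 says "SinuSonic is a medical device that utilizes sound and pressure combined with normal breathing". How far breathing differs between the readings is therefore unknown. The point needs only that the device readings follow an instructed exhalation and the reference does not.

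Nor is it right that the frequencies tell nothing about sound. A difference between them would be acoustic evidence, and the repeated-measures ANOVA with post-hoc tests in section 10.0 could carry that comparison. But the Aim 1 comparisons actually named there are with baseline only, and the form has no place to record frequency.

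Finally, this is a 10-subject part of an exploratory pilot, and no stated decision rests on it. That limits the weight of the point. It does not remove it, because subjects serve as their own controls and a matched reading costs minutes.

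**Conclusion.** The point holds as a limit on attribution. As planned, a rise in NO shows an effect of device use as a whole. It cannot separate the combined vibration and oscillating pressure from the manoeuvre, mask and order, and it cannot isolate sound. The randomised frequencies offer partial acoustic evidence that the named analysis does not use.

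The size of the bias cannot be worked out from the documents. A reader might want to state by what factor the acoustic effect is overstated, but that needs the share of the rise due to breathing, which is not given. The probabilities in the working (0.29 to 0.99 for an assumed 0.5 to 1.5 SD) are illustrative only.

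The conclusion rests on the resting reading coming first, as section 3.0 describes. What is said of the frequencies also rests on the four devices sharing the same valve and manoeuvre, which the plan does not state. Given the pilot setting, this is an inexpensive improvement and not a flaw that invalidates Aim 1.

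**What to change.** Keep the resting value and make these changes:

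1. Add to the randomised sequence a matched-breathing reading: the same two nasal exhalations, to the same depth, without the device, then the same 30-second sampling.
2. If the speaker can be switched off, which the documents do not say, include one sound-off device trial in the randomised sequence, either added or replacing one frequency.
3. Prespecify in section 10.0 the contrasts of device against matched breathing (combined effect), sound-on against sound-off (acoustic effect), and between frequencies. Add a field for condition and frequency to the Aim 1 form.
4. If no sound-off trial is possible, limit the conclusion to the device as a whole. The matched-breathing reading removes the manoeuvre and the order of readings but leaves mask, resistance and sound together.

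**Cost.** Each added trial takes a 5-minute rest and 30 seconds of sampling, 5.5 minutes. One added trial makes the visit about 6 minutes longer and two make it 2 × 5.5 = 11 minutes longer, for 10 subjects in a visit already planned. If the sound-off trial replaces a frequency, only the matched-breathing reading adds time, at the price of one fewer frequency. No new staff or type of procedure is needed.

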10.0 Data Management

All analyses and graphs will be performed with SPSS 24.0, Sample Power 3.0, and Sigma Plot 10.0 (SPSS, Chicago, IL.). Disease information and demographic variables, such as age, gender, race, quality of life (QOL) scores, and VAS scores will be summarized using frequencies, means, and standard deviation as appropriate. Aim 1 nasal NO metrics will be compared between baseline vs 10 seconds and baseline vs 3 minutes. Aim 2 metrics (ETDQ-7, ETD VAS and tympanogram) will be compared between baseline and 6 weeks. Aim 3 metrics (VAS, BPI-SF, MCQ-SF) will be compared between baseline vs 2 weeks and baseline vs 4 weeks. Categorical variables will be compared using Chi Square or McNemar's test. Continuous variables will be compared using One-Way ANOVA with repeated measures follow by post-hoc analysis. Data regarding safety and patient satisfaction will be summarized for each time point. A p-value ≤ 0.05 will be considered statistically significant. Due to the exploratory nature of this study, no p-value correction (ie Bonferroni) will be applied.

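### Aim 1 specifies no return-to-baseline check between nasal NO trials, and the 1-minute 128 Hz trial is always last, so its effect cannot be separated from its position

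*Combined protocol and SAP*

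**What the plan says.** Section 3.0 gives the Aim 1 session in four steps. First, "Baseline exhaled nasal NO will be measured using a clinically available nasal airflow sampling device at rest". The device trials follow: "Then using SinuSonic devices for 2 exhalations followed by the 30 second NO sampling period". On order, "We will use 4 SinuSonic devices with frequencies between 64Hz and 2,000Hz in random order". On spacing and the last trial, "Five minutes rest will be allowed between trials. The final trial will use 128 Hz for 1 minute". The section ties no NO reading to the end of a rest, sets no criterion for return to baseline, and gives no reason for the fixed last position.

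Three other places bear on the point, and they agree neither with section 3.0 nor all with one another:

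- The schedule in section 9.1 lists NO on Day 0 at 30 seconds and at 5 minutes. The 5-minute reading is not explained.
- Section 10.0 states that "Aim 1 nasal NO metrics will be compared between baseline vs 10 seconds and baseline vs 3 minutes". The method is repeated-measures ANOVA with post-hoc tests, and no period, sequence or carry-over term is mentioned.
- The Aim 1 form in the appendix has fields for resting, 10-second and 3-minute peaks. The same fields recur on a Day 1 repeat form, although section 3.0 and the schedule have no Day 1 visit. Neither form has a field for a frequency, a 30-second sample, a 5-minute reading or a 1-minute trial.

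**The concern.** The design relies on a 5-minute rest as washout, but the documents give no recovery time for nasal NO and specify no reading that would show recovery. The plan's own rationale (section 2.0) is that acoustic energy raises nasal NO strongly and that gas moves between the sinuses, the middle ear and the nose. On that premise an earlier exposure could leave nasal NO raised, or could leave less gas to be released.

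Randomising the order spreads position effects over the four short trials only. Baseline is always first and the 1-minute trial always last. A rise from baseline in that last trial could come from the device, the longer exposure, time in the session, or residue from four earlier exposures. Under section 3.0 this is the Aim 1 exposure closest in length to the 3-minute use in Aims 2 and 3, so it is the one most likely to be cited as evidence of mechanism.

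**Working it through.** The plan has no sample-size or power calculation for Aim 1, so there is no figure to reproduce. The check covers the structure and timing, then adds an illustration.

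**Timing.** The inputs, all from section 3.0, are four short trials, 30 seconds of sampling in each, and a 5-minute rest between trials. The final trial is read as a fifth exposure, which is natural but not stated. From the end of baseline to the start of the final trial:

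4 × 0.5 min + 4 × 5 min = 2 + 20 = 22 min.

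This is a minimum, because the time for the exhalations is left out.

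**Structure.** Number the positions 0 (baseline), 1 to 4 (random order) and 5 (final). Position 5 and the 1-minute trial coincide in every subject. A period term would not help, because the indicator for period 5 and the indicator for the 1-minute trial are the same column. Whether 128 Hz is also one of the four randomised devices is not stated, so frequency may be mixed in as well.

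**Drift (assumed).** Let NO drift by b per position, in SDs of the paired difference, with no device effect.

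- Final minus baseline shifts by 5b.
- The four short trials have mean position (1 + 2 + 3 + 4)/4 = 2.5, so their mean minus baseline shifts by 2.5b.
- Final minus the mean of the four also shifts by 5b − 2.5b = 2.5b.
- Contrasts among the four short trials have an expected shift of zero.

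The chance of p ≤ 0.05 is taken from the noncentral t distribution for a two-sided paired t-test with n = 10 (9 degrees of freedom, noncentrality = shift × √10). Section 10.0 gives the 0.05 level; two-sided testing is assumed. The same SD unit is used for both contrasts, which is a simplification.

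| b (assumed) | Final − baseline | Chance p ≤ 0.05 | Mean of four − baseline | Chance p ≤ 0.05 |
|---|---|---|---|---|
| 0 | 0 | 5.0% | 0 | 5.0% |
| 0.05 | 0.25 SD | 10.9% | 0.125 SD | 6.5% |
| 0.10 | 0.50 SD | 29.3% | 0.25 SD | 10.9% |
| 0.20 | 1.00 SD | 80.3% | 0.50 SD | 29.3% |

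**Carry-over (assumed).** Let a fraction r of each trial's effect survive each rest, with equal effects per trial. Carry-over into the final trial is r + r² + r³ + r⁴. For r = 0.10 this is 0.1 + 0.01 + 0.001 + 0.0001 = 0.11 of one trial's effect. Carry-over into positions 1 to 4 is 0, 0.1, 0.11 and 0.111, with a mean of 0.08.

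| r (assumed) | Carry-over into final trial | Mean over positions 1–4 |
|---|---|---|
| 0 | 0 | 0 |
| 0.10 | 0.11 | 0.08 |
| 0.25 | 0.33 | 0.22 |
| 0.50 | 0.94 | 0.53 |

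The sign reverses if earlier trials deplete the gas available instead of leaving it raised. The documents give no SD, drift or recovery time from which to choose a row.

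**The case against.** A reader might infer that return to baseline is never checked. The documents do not support that. The 5-minute reading in the schedule equals the rest interval and could be a post-rest check, and the Day 1 form has a second resting peak. What can be said is that no between-trial check is specified: the 5-minute reading is undefined, has no form field and is absent from the analysis, and a Day 1 value could not show recovery within the Day 0 session. Nor does the form prove that the session has a single resting reading, because its fields do not fit the five-trial session at all.

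A reader might also infer that the final trial carries all of the error. It does not. Baseline is always first, so the short trials share the problem; under linear drift their mean shifts by half as much as the final trial. Nor does the plan state that the 1-minute trial will be tested against baseline or against the short trials. Section 10.0 names neither contrast, so the drift percentages show what would happen if such a test were run.

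Three further objections have weight. Putting the longest exposure last keeps its residue out of the randomised trials, which is a sound reason for the order. The illustrated sizes are assumptions, and zero is possible. Aim 1 is a 10-person mechanism check in a pilot whose analysis the plan calls exploratory. These points lower the priority. They do not supply a washout check, nor do they separate the final trial from its position.

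**Conclusion.** The concern holds in this form. As section 3.0 describes the session, one resting reading precedes all device use and no check of recovery between trials is specified. Any drift or residual effect enters every device-versus-baseline contrast. If it accumulates, it is greatest for the 1-minute 128 Hz trial, where no analysis of the planned readings can separate it from the trial's effect. Random order protects only contrasts among the four short trials, and does so in expectation.

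The 22-minute minimum rests on counting the final trial as a fifth exposure. The size of any bias cannot be judged from the documents, and it may be zero. A claim that 5 minutes is too short, or that the NO results will be biased by a given amount, would go beyond them. The consequence is limited to the interpretation of Aim 1; Aims 2 and 3 are unaffected. The point deserves action mainly because the remedy is cheap.

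**What to change.** Take a 30-second resting NO reading with the same sampler at the end of each existing 5-minute rest. Defining the schedule's 5-minute reading in this way would serve. Record it on the form beside its trial. Compare each trial with its own pre-trial resting value; the baseline reading serves the first trial. Report the resting values in sequence as the washout check.

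The 1-minute trial may stay last. Report it as change from its own pre-trial value, and make no comparison with the short trials as an effect of duration. Pre-trial readings address residual elevation and resting drift, but a resting reading cannot exclude depletion of the sinus pool, which would show only on exposure.

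Reconcile the Aim 1 NO time points across section 3.0, the schedule in section 9.1, section 10.0 and the Aim 1 appendix forms, so that the readings taken, recorded and analysed are the same ones.

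The cost is four extra readings, 4 × 0.5 = 2 minutes of sampling per subject, or 20 minutes over 10 subjects, all inside existing rests, plus added form lines. The downside is a slightly greater sampling burden.

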4.0 Inclusion and Exclusion Criteria/ Study Population

Aim 1 exhaled NO: For the exhaled NO portion of the study, we will examine 10 healthy control patients with no symptoms of upper airway infection, inflammation or ETD to determine impact of SinuSonic upon NO release.

Inclusion Criteria

- -Adults 18 years or older with no symptoms of URI, ETD or other ENT conditions

Exclusion Criteria

- Sinonasal or ear surgery within last 3 months (including balloon ET dilation)
- Any ENT condition that may impact upper airway to include sinusitis, otitis, or allergies
- Upper respiratory illness within last 2 weeks
- Topical decongestant use in last week
- Current nasal crusting or ulceration on rhinoscopy
- History of severe nose bleeding within last 3 months
- Known pregnancy
- Allergic sensitivity to silicone or any other component of device
- Inability to read and understand English
- Inability to perform treatment due to underlying medical condition

Aim 2 ETD efficacy: The ETD study population will consist of individuals presenting for care at the Otolaryngology clinics at the Medical University of South Carolina with ETD, or from the community at large.

Inclusion Criteria

- -Adults 18 years or older with diagnosis of ETD by an otolaryngologist

- ≥ 6 months of symptoms duration
- ≥ 3 ETD symptoms (ear pressure, feeling that ears are clogged, cracking/popping of ears, muffled hearing, tinnitus)
- ETDQ-7 score ≥ 3
- Audiogram within the last year

Exclusion Criteria

- Sinonasal or ear surgery within last 3 months (including balloon ET dilation)
- Indwelling ear tubes
- Tympanic membrane perforation
- Hx of cholesteatoma, mastoidectomy, tympanoplasty, or ossicular chain reconstruction
- Patulous ET
- Hx of Meniere's disease
- Moderate or severe nasal valve collapse
- Grade 3-4 polyps
- Upper respiratory illness within last 2 weeks
- Topical decongestant use in last week
- Current nasal crusting or ulceration on rhinoscopy
- History of severe nose bleeding within last 3 months
- Known pregnancy
- Allergic sensitivity to silicone or any other component of device
- Inability to read and understand English
- Inability to perform treatment due to underlying medical condition

Aim 3 Facial pain/pressure efficacy: The facial pain/pressure study population will consist of individuals presenting for care at the Otolaryngology clinics or community at large with self-reported sinus pain/pressure.

Inclusion Criteria

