- -Adults 18 years or older who complain of facial pain or pressure
- ≥ 3 months of symptoms duration (can be intermittent)
- Pain/pressure VAS score ≥ 5

Exclusion Criteria

- Sinonasal surgery within the last 3 months
- Grade 3-4 polyps
- Upper respiratory illness within last 2 weeks
- Topical decongestant use in last week
- Current nasal crusting or ulceration on rhinoscopy
- History of severe nose bleeding within last 3 months
- Known pregnancy
- Allergic sensitivity to silicone or any other component of device
- Inability to read and understand English
- Inability to perform treatment due to underlying medical condition

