|---|------------------------------|-----------------------------|
|  Nasal steroid sprays (Flonase, Nasonex, etc) |  Yes |  No |
|  Nasal antihistamine spray (Astelin, etc) |  Yes |  No |
|  Oral antihistamines (Allegra, Claritin, Benedryl, etc) |  Yes |  No |
|  Oral decongestant (Sudafed, etc) |  Yes |  No |
|  Mucolytic (Mucinex, etc) |  Yes |  No |
|  Luekotriene (Singulair, etc) |  Yes |  No |

COMORBID MEDICAL CONDITIONS: Check box and provide details if present

- ☐ Depression history: ☐ Resolved/past diagnosis ☐ Present/medicated ☐ Present/not medicated
- ☐ Anxiety history: ☐ Resolved/past diagnosis ☐ Present/medicated ☐ Present/not medicated
- ☐ Obstructive Sleep Apnea: ☐ Currently being treated ☐ History / No current treatment
- ☐ Allergic rhinitis: _____
- ☐ Previous allergy testing (blood test or skin prick): ☐ Yes ☐ No
- ☐ Immunotherapy shots for allergies: ☐ Yes ☐ No ☐ Currently
- ☐ Non-allergic rhinitis ☐ Yes ☐ No
- ☐ Asthma ☐ Yes ☐ No
- ☐ Chronic rhinosinusitis ☐ Yes ☐ No
- ☐ Nasal polyps ☐ Yes ☐ No
- ☐ Viral respiratory infection ☐ Yes ☐ No
- ☐ Prior ear/sinus surgery ☐ Yes ☐ No
- ☐ Migraine headache history: ☐ Resolved/past diagnosis ☐ Present/medicated ☐ Present/not medicated

- _____
- ☐ Height (ft/in): _____
- ☐ Weight (lbs): _____

Rhinoscopy:

Septal Deviation: None Mild Moderate Severe Nasal

valve collapse: None Mild Moderate Severe Bleeding:

None Yes

[figure not shown]
Crusting: None Yes

Otoscopy: Normal Abnormal findings:_____

[figure not shown]
AIM 3, SINUS PAIN/PRESSURE: Baseline questionnaires

PATIENT QUESTIONS	
How long have you had sinus or facial pain/pressure? <3 months 3-6 months 6-12 months 1-3 year >3 years	
OVER THE LAST WEEK, HOW WOULD YOU RATE YOUR AVERAGE SINUS OR FACIAL PAIN/PRESSURE?	
	None possible Worst
Sinus or facial pain/pressure	◆—————◆

INCLUSION CRITERIA (all must be yes):Does patient have sinus pain/pressure for ≥ 3 mos? Yes NoIs VAS score ≥ 5 ? Yes No

AT THIS EXACT MOMENT, HOW WOULD YOU RATE YOUR SINUS OR FACIAL PAIN/PRESSURE?	

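### In Aim 3, and less certainly in Aim 2, the qualifying score is also the analysis baseline of a single-arm test, so regression to the mean alone can give p ≤ 0.05 and the test cannot establish efficacy

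*Combined protocol and SAP*

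**What the plan says.** **Aim 3.** Section 3.0: "Subjects will complete VAS to confirm eligibility". Section 4.0 requires "Pain/pressure VAS score ≥ 5" and admits patients with "≥ 3 months of symptoms duration (can be intermittent". In the appendices, the Aim 3 baseline form asks, for the last week, "HOW WOULD YOU RATE YOUR AVERAGE SINUS OR FACIAL PAIN/PRESSURE", and the eligibility check stands directly below that item. The same last-week item returns on the 2-week and 4-week forms, and section 10.0 compares both with baseline.

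**Aim 2.** Section 3.0: "Subjects will complete ETD questionnaire to confirm eligibility". Section 4.0 requires "ETDQ-7 score ≥ 3", without saying whether this is a mean item score or a total. The appendix prints the check below the baseline ETDQ-7. Section 10.0: "Aim 2 metrics (ETDQ-7, ETD VAS and tympanogram) will be compared between baseline and 6 weeks".

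**Both aims.** The schedule in section 9.1 has one pre-treatment column, week 0, for screening and baseline together. Every patient gets the device, and no control or sham arm is described. Section 10.0 specifies repeated-measures ANOVA with post-hoc tests at p ≤ 0.05, uncorrected. The Aim 3 objective in section 1.0 is "To determine the safety and efficacy of combined acoustic vibration and oscillating expiratory pressure for treatment of sinus pain/pressure", and Aim 2 has the same wording for ETD.

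**The concern.** A patient whose qualifying score is high partly through a bad week or measurement error will tend to score lower next time, whatever happens in between. When that score is also the baseline, the expected change is negative even with an inert device, and a test against zero change counts the fall as improvement. With no comparator, nothing in the analysis separates this fall from a device effect.

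At stake are the efficacy conclusion, above all in Aim 3, and the size of any effect carried into a later trial. The direct effect is on the last-week VAS and the ETDQ-7. The BPI-SF, MPQ-SF, ETD VAS and tympanogram carry no score cut-off and are affected only as far as they correlate with the qualifying score. The entry rule of at least three ETD symptoms does overlap with the ETD VAS items.

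**Working it through.** The plan gives no power, effect size or sample-size calculation, so there is no figure of its own to reproduce.

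**Inputs from the documents:** n = 30 per aim (section 5.0); cut-offs 5 and 3 (section 4.0); one baseline reading (section 9.1); α = 0.05 and a no-change null (section 10.0). Sidedness is not stated, so I take two-sided, which is 2.5% in the direction of improvement.

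**Assumed, because the documents do not give them:** VAS 0–10, SD 2, screened mean 4 to 7; ETDQ-7 as a mean item score, SD 1.2, screened mean 3 to 5; test-retest correlation r from 0.6 to 0.8; normal scores with errors independent between readings; no device effect and no time trend.

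**Formulas.** Let a = (cut-off − mean)/SD and λ = φ(a)/(1 − Φ(a)).

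- Expected fall = SD × (1 − r) × λ
- Variance of the change among those selected = (1 − r)² × SD² × (1 + aλ − λ²) + SD² × (1 − r²)
- Smallest significant mean change at n = 30: 2.045/√30 = 0.37 SD of the change
- False-improvement rate ≈ P(Z > 2.045 − √30 × fall/SD of change)

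**Aim 3, middle case (mean 5, r = 0.7).** a = 0 and λ = 0.798. Fall = 2 × 0.3 × 0.798 = 0.48 points. Variance = 0.09 × 4 × 0.363 + 4 × 0.51 = 2.17, so SD = 1.47. Shift = √30 × 0.479/1.473 = 1.78. Rate ≈ P(Z > 0.265) ≈ 40%; simulation gives 41%. Counting significance at either week 2 or week 4 raises it to 58%.

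**Aim 3, adverse end (mean 4, r = 0.6).** a = 0.5 and λ = 1.141. Fall = 2 × 0.4 × 1.141 = 0.91. SD of change = 1.65, shift = 3.02, rate ≈ P(Z > −0.98) ≈ 84%.

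**Aim 3, mild end (mean 7, r = 0.8).** a = −1 and λ = 0.288. Fall = 2 × 0.2 × 0.288 = 0.12. SD of change = 1.24, shift = 0.51, rate ≈ 6%; simulation, with scores clipped to the scale, gives about 7%.

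| Screened mean VAS | Share meeting cut-off | r | Expected fall | False improvement (simulated) |
|---|---|---|---|---|
| 4 | 31% | 0.6 | 0.91 | 84% |
| 4 | 31% | 0.8 | 0.46 | about 50% |
| 5 | 50% | 0.6 | 0.64 | 53% |
| 5 | 50% | 0.7 | 0.48 | 41% |
| 6 | 69% | 0.8 | 0.20 | 14% |
| 7 | 84% | 0.8 | 0.12 | about 7% |

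**Aim 2, mean item score.** At mean 3 and r = 0.6, the fall is 1.2 × 0.4 × 0.798 = 0.38, and the simulated rate is 53%. At mean 5 and r = 0.8, a = −1.67 and λ = 0.104; the fall is 1.2 × 0.2 × 0.104 = 0.03, and the rate is about 4%.

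**Aim 2, total score.** Seven items scored 1 to 7 have a minimum total of 7 × 1 = 7, so a cut-off of 3 excludes nobody. Simulation then gives 2.4% in the device's favour, which is nominal.

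**Check of the remedy.** In the same simulations, qualifying on one reading and using a separate later reading as baseline brings the mean change to about 0 and two-sided rejection to about 5%. This relies on errors being independent between readings. If symptoms drift slowly, a week's gap removes only part of the regression.

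**The case against.** The strongest reply has four parts.

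*The sizes are assumption-driven.* This stands. The documents give no SD, correlation, screened distribution or VAS range. The 84% figure needs a screened mean of 4, at which about 69% of those screened would fail the cut-off. On a 0–100 line a cut-off of 5 would truncate little. The item is already a one-week average, and recent upper respiratory illness is excluded; both damp fluctuation. A reader might infer that a significant result is to be expected without any device effect. The documents support only that it can occur; it is likely only in the more adverse settings.

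*Aim 2 is not the same case.* This stands too. Those patients need an otolaryngologist's diagnosis, at least 6 months of symptoms and at least three symptoms, so many may score well above 3. A reader might treat both aims alike, but in Aim 2 the effect is near nominal if the screened mean is about 5, and absent if the cut-off is a total.

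*Not every endpoint is selected on.* Also correct. A reader might infer that all outcomes of both aims are biased to the same degree, but those without a cut-off are affected only through correlation.

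*It is an exploratory pilot with no success threshold or go/no-go rule.* This lowers the stakes but does not answer the point. Section 10.0 uses exploratory status only to omit p-value correction, while section 1.0 still sets out to determine efficacy and section 10.0 fixes a significance level.

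**Conclusion.** The point holds, firmly for Aim 3 and weakly for Aim 2. The structure is plain in the documents: one reading qualifies the patient and serves as baseline, there is no comparator, and the null is no change. Under the assumptions above, regression to the mean alone gives a false improvement in about 7% to 84% of trials for the last-week VAS. For ETDQ-7 it is about 4% to 53% as a mean item score, and nominal as a total. These are illustrative ranges, not estimates for this trial. They exclude natural history and placebo response, which the design also leaves uncontrolled. None of this shows that the device does not work; it shows that p ≤ 0.05 against baseline cannot establish that it does.

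**What to change.** **1. Claim and reporting, Aims 2 and 3.** In section 1.0, replace the goal of determining safety and efficacy with assessing safety and estimating within-subject change. In section 10.0, report each change with a 95% confidence interval, and state that p ≤ 0.05 against baseline is not evidence of device efficacy because regression to the mean, natural history and placebo response are not controlled. Cost: a more modest claim and almost no work. This can be done at any time before analysis.

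**2. Separate baseline, Aim 3.** After consent, take a second last-week VAS at least one week after the qualifying one, so that the recall windows do not overlap, and before first device use. Use it as the analysis baseline whatever its value. Cost: about a week's delay, some baselines below 5 and, for patients recruited at a clinic appointment, possibly a return visit or a remote start, since section 3.0 places the first device use in the clinic. At the $50 per visit in section 15.0, return visits for all 30 would cost at most 30 × $50 = $1,500 and would take the maximum per patient from $150 to $200. This must be settled before enrolment, because a pre-treatment reading cannot be recovered later.

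**3. Aim 2.** State whether the ETDQ-7 cut-off is a mean item score or a total. If it is a mean item score, a second reading would need at least a one-month gap because of the one-month recall. If that is impractical, rely on item 1.

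Printing an expected regression beside the observed change is not recommended. It needs a test-retest correlation that the plan does not supply, and under the model above it is about zero once the readings are separated.
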